Title: *An evaluation of the effect of an angiotensin-converting enzyme (ACE) inhibitor on the growth rate of small abdominal aortic aneurysms*

AARDVARK [Aortic Aneurysmal Regression of Dilation : Value of Ace-inhibition on Ris K](#)

Objectives:

1. To investigate the hypothesis that an ACE-inhibitor reduces abdominal aortic aneurysm (AAA) growth rate. In a pilot 3-arm randomised controlled trial: The three interventions are ACE-inhibition with perindopril versus equivalent blood pressure reduction with amlodipine (a calcium channel blocker) versus placebo. By comparing the effects in the perindopril and amlodipine arms, this design will permit an evaluation of any blood pressure independent effects of perindopril.
2. Pending results of the pilot trial, to work with the local and National Aneurysm Screening programme to conduct a larger, definitive 3-arm randomised controlled trial, to investigate the hypothesis that blood pressure reduction with an ACE-inhibitor slows the rate of small AAA growth preferentially compared with other antihypertensive agents. Aneurysm-related mortality, morbidity and quality of life will be the major secondary end-points.

The pilot trial will recruit approximately 225 patients from aortic aneurysm screening sites in or near to London. They will be seen and assessed with an ultrasound examination every three months for a period of 24 months.

(i) Inclusion criteria

[figure not shown]
(ii) All men or women, aged OVER 60 years, with AAA between 3.0 and 5.5 cm and with a systolic BP <150mmHg will be eligible for inclusion in the trial unless they are routinely already receiving an ACE-inhibitor or amlodipine 10mg daily. For patients whose systolic BP is >150mmHg, a 6 week course of the diuretic indapamide SR (1.5mg daily) will be given, with re-evaluation of BP in the 6th week: If the SBP falls to <150mmHg on this medication subjects would then be eligible for inclusion into the study. If this diuretic treatment is not appropriate then 5mgs of amlodipine could be prescribed by the patients GP if not already taking this drug. This would be followed by a six week re-evaluation as above.

(ii) Exclusion criteria

1. Patients who cannot be converted to diuretic therapy and/or lower doses of amlodipine or patients already taking an angiotensin II antagonist (ARB) for the treatment of blood pressure.
2. those with known renal artery stenosis (>50%), or with a serum creatinine > 180umol/L on routine testing.
3. those unable to give informed consent
4. those too frail to travel for 3-monthly surveillance will be excluded.
5. Any clinically significant medical condition which, in the opinion of the investigator, may interfere with the study results;
6. Participation in another trial of an investigational product or device within the previous 30 days;
7. Known allergy or sensitivity to perindopril or amlodipine
8. Unable or unwilling to comply with the requirements of the study, in the opinion of the investigator.

	Local screening centre staff	Screen & Consent Project co-ordinator And medical investigator	Randomisation Project co-ordinator	Treatment Project co-ordinator								
Visit	-2 Suitable patients identified and contacted	-1 AAA 3.0-5.4cm? SBP<150mmHg ?	1 (Baseline) Either 1 week after blood test or 6 weeks after starting indapamide	2	3	4	5	6	7	8	9	
Months		-2 to 0.25	0	3	6	9	12	15	18	21	24	
Inclusion & exclusion criteria		X	check									
Informed consent		X	check									
Demography		X										
Past medical history		X										
Current medical therapies		X	check	X	X	X	X	X	X	X	X	
Ultrasound of AAA	AAA 3.0-5.4cm?	review	X	X	X	X	X	X	X	X	X	
Blood pressure		X	X	X	X	X	X	X	X	X	X	
Adverse events				X	X	X	X	X	X	X	X	
Pill count				X	X	X	X	X	X	X	X	
Blood for creatinine and electrolytes		X	review	X			X				X	
Blood for lipid profile		X	review check lipid lowering prescribed									
EuroQoL, health resource questionnaire								X			X	

Project Timetable and Milestones

Total trial length = 42 months.

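### Do the 5.5 cm and 5.4 cm aneurysm limits, and the unassigned systolic pressure of exactly 150 mmHg, call for a change to the eligibility rules?

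*Protocol*

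**What the plan says.** **Aneurysm diameter.** The inclusion paragraph of the protocol admits patients "with AAA between 3.0 and 5.5 cm and with a systolic BP <150mmHg". It does not say whether the two end values belong to the range, and the visible text gives no recording precision. The visit schedule states a limit in two places: the heading of Visit -1, "AAA 3.0-5.4cm? SBP<150mmHg", and the ultrasound row at Visit -2, "Ultrasound of AAA AAA 3.0-5.4cm".

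**Systolic pressure.** Three statements in the inclusion paragraph use 150 mmHg, each with a strict inequality:

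- direct entry: "with a systolic BP <150mmHg will be eligible for inclusion in the trial"
- run-in: "For patients whose systolic BP is >150mmHg, a 6 week course"
- re-evaluation after the run-in: "If the SBP falls to <150mmHg on this medication subjects would then be eligible"

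The schedule repeats only the first of these, as a yes/no question at Visit -1. Its baseline column allows for two timings: one week after the blood test, or six weeks after starting the diuretic.

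A figure under the first inclusion heading is not shown in the text available for review, and it may bear on either point.

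**The concern.** An eligibility rule should give one answer for each patient, and here two places give different upper limits. The 5.4 cm figure appears twice, so a single typing slip is a less likely explanation. At Visit -1 the same staff work under the 5.4 cm heading and also tick the inclusion criteria, which say 5.5 cm. A patient measuring 5.5 cm could be accepted on one statement and turned away on the other. The question can return at baseline, where the schedule has a new ultrasound and a further check of the criteria, up to two months after screening.

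For blood pressure, the two strict inequalities leave a hole at 150, a round number that staff may well record. Sites might handle it differently, some offering the run-in and others not.

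At stake would be uneven enrolment across sites and arguments over whether particular patients were protocol deviations. A statistical analysis plan would not normally settle such matters.

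**Working it through.** The documents give no figure to reproduce here. The check compares the statements at their boundaries, then sizes what is left.

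**1. Aneurysm range, by reading of the inclusion paragraph (schedule: 3.0 to 5.4 cm; diameters to 0.1 cm)**

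| Reading of the written range | Eligible by criterion | Conflict with schedule |
|---|---|---|
| Both ends included | 3.0 to 5.5 | 5.5 only |
| Both ends excluded | 3.1 to 5.4 | 3.0 only |
| 3.0 included, 5.5 excluded | 3.0 to 5.4 | none |

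So one ordinary reading reconciles the two statements exactly, and each of the other two leaves a single recorded value in dispute. Recording to the whole millimetre adds nothing: 5.4 cm is 54 mm, 5.5 cm is 55 mm, and no whole number lies between them. Only sub-millimetre recording would open a gap, and the visible text describes none.

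**2. Direction of any error.** The schedule's check is the narrower one at the top. Under the first and third readings, everyone who passes it also meets the written criterion, so nobody is wrongly screened in; at most a 5.5 cm patient is not referred. A patient who passes the schedule but fails the criterion arises only under the second reading, and only at exactly 3.0 cm.

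**3. Growth between screening and baseline.** Growth rate is an assumption, taken as 1 to 4 mm/year. Over two months:

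- 1 × 2/12 = 0.17 mm
- 4 × 2/12 = 0.67 mm

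A patient screened at 54 mm would then be at 54.17 to 54.67 mm, before measurement error. The faster rate could produce a baseline reading of 55 mm, the same boundary value as in step 1.

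**4. Follow-up beyond the entry range.** At the same assumed rates, growth over the first three months is 1 × 0.25 = 0.25 mm to 4 × 0.25 = 1 mm, so a patient entering at 5.5 cm would soon exceed it. That costs no data. The range is an entry criterion, ultrasound is scheduled every three months to month 24, and nothing visible discards later scans. At 4 mm/year a 5.4 cm patient also reaches 5.5 cm at the first scan, so this is not a consequence of the mismatch.

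**5. Systolic pressure of exactly 150.**

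- Direct entry needs a value below 150. 150 is not below 150, so the answer is no.
- Run-in is stated for values above 150. 150 is not above 150, so it is not named.
- Re-evaluation needs a value below 150. A patient at 150 there is not eligible.

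The test for entering the trial is therefore complete at 150. What is unstated is whether the run-in is open to that patient.

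**6. How often 150 might be recorded.** The documents give no distribution. Assume a normal distribution with mean 135 to 145 and SD 15 to 20 mmHg. The share recorded as 150 with rounding width w is Φ((150 + w/2 − mean)/SD) − Φ((150 − w/2 − mean)/SD).

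| Rounding | Lowest (mean 135, SD 20) | Highest (mean 145, SD 15) |
|---|---|---|
| 1 mmHg | 1.5% | 2.5% |
| 2 mmHg | 3.0% | 5.0% |
| 10 mmHg | 15.0% | 24.8% |

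These are shares of patients screened, not of patients randomised, and they rest wholly on the assumed distribution and rounding. Nothing in the protocol suggests reading to the nearest 10 mmHg.

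**The case for a change.** The best case for acting is that the fix costs only wording, that eligibility is decided by different staff at several screening sites, and that two versions of a limit invite different practice. The reconciling reading is nowhere stated, so staff must infer it. The baseline check adds force, because a patient screened in at 5.4 cm may measure 5.5 cm at baseline, where the outcome depends on whether 5.5 cm is inside the range. For blood pressure, 150 is a value that will occur, and different sites may treat it differently.

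The facts in this stand: the end-points and the precision are unstated, and the run-in branch omits one value. What does not follow is harm to the trial. Inconsistent practice at the boundary changes which few patients are offered entry. It does not change how patients are allocated, measured or compared. At 150 mmHg, the schedule's yes/no check and its two baseline timings already lead staff towards a workable handling, and no one is randomised in breach of the pressure criterion through the gap.

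**Conclusion.** No change to the plan follows. The mismatch is real but clerical, and sites can be expected to handle the boundary values sensibly.

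Its size is one recorded diameter at an end of the range, or none under the reading that includes 3.0 cm and excludes 5.5 cm, together with one pressure value for which only access to the run-in is undefined. Any one patient is 1/225 = 0.4% of the recruitment target. Because eligibility is settled before randomisation, the choice at the boundary cannot favour an arm, and the comparison of growth rates stands if the plan is followed as written.

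This rests on diameters being recorded to 0.1 cm and on the visible text, since the figure under the inclusion heading might already settle the limits. The inclusion paragraph and the schedule should be reconciled when the protocol is next edited. Which diameter limit is intended, and which branch covers 150 mmHg, are the sponsor's decisions, and this review takes no position on them.

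### Exclusion 1, read literally, bars ARB users only when the ARB is taken for blood pressure, so a patient on an ARB for another reason could be randomised and modestly dilute the perindopril contrasts

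*Protocol*

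**What the plan says.** Two drug classes that act on the angiotensin pathway are handled by differently worded entry rules.

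- **ACE-inhibitors.** The inclusion paragraph, numbered (ii), admits patients with a qualifying aneurysm and systolic pressure "unless they are routinely already receiving an ACE-inhibitor or amlodipine 10mg daily". No indication is named for the ACE-inhibitor.
- **ARBs.** The only visible mention is the second limb of exclusion 1, which removes "patients already taking an angiotensin II antagonist (ARB) for the treatment of blood pressure". Here an indication is named.

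Exclusion 1 opens with a separate limb, "Patients who cannot be converted to diuretic therapy and/or lower doses of amlodipine", which does not say which drugs the patient would be converted from.

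Three other provisions bear on the point:

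- Exclusion 2 removes "those with known renal artery stenosis (>50%), or with a serum creatinine > 180umol/L on routine testing".
- Exclusion 5 removes "Any clinically significant medical condition which, in the opinion of the investigator, may interfere with the study results".
- The visit schedule has a row for "Current medical therapies", marked at Visit -1, checked at baseline and marked at every later visit.

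Objective 1 sets the purpose: "By comparing the effects in the perindopril and amlodipine arms, this design will permit an evaluation of any blood pressure independent effects of perindopril".

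**The concern.** The ARB rule turns on why the drug was prescribed. For the trial's question, what matters is whether the patient is already under angiotensin blockade. That is the same whether the ARB was given for blood pressure or for something else, such as heart failure or kidney disease. The ACE-inhibitor rule already uses the more suitable test, current routine use.

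If a patient on a continuing ARB is randomised, perindopril may have less left to add. Perindopril versus placebo and perindopril versus amlodipine would then both shrink somewhat. The amlodipine comparison carries the claim about effects independent of blood pressure, so a pilot meant to inform a larger trial has some interest in keeping it clean.

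**Working it through.** **Step 1. Follow one patient through the visible rules.** Take a patient on an ARB for a reason other than blood pressure, with no ACE-inhibitor, no amlodipine 10 mg and systolic pressure below 150 mmHg.

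| Rule | Does it remove this patient? |
|---|---|
| Inclusion paragraph (ii) | No. It names ACE-inhibitors and amlodipine 10 mg, not ARBs. |
| Exclusion 1, first limb | Not clearly. It concerns patients who cannot be switched and names no drug to switch from. |
| Exclusion 1, second limb | No, read literally. The indication does not match. |
| Exclusion 2 | Only with known renal artery stenosis above 50% or creatinine above 180 umol/L. |
| Exclusion 5 | Possibly. It concerns a condition, not a drug, and rests on the investigator's opinion. |
| Schedule, therapies row | No. It would show the ARB before randomisation, but no visible rule attaches an exclusion to it. |

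Nothing visible requires the ARB to be stopped.

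**Step 2. Size of the dilution.** There is no figure in the plan to reproduce. The sample size of approximately 225 is given without power, significance level, effect size, standard deviation or ARB share. What follows is an illustration.

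Inputs:

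- N = 225 (Protocol, text after the objectives).
- f = share of patients entering on a continuing ARB for another reason. Assumed 1%, 2% and 5%.
- r = share of perindopril's added effect lost in those patients. Assumed 0.5 (half) and 1 (all).
- Undiluted power of 80% or 90%, two-sided 5%. Assumed.

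Formulas:

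- Retained effect m = 1 - f × r
- Diluted power = Φ((1.960 + z) × m - 1.960), with z = 0.8416 for 80% and 1.2816 for 90%
- Equivalent sample size = 225 × m²

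Arm size and standard deviation cancel once a starting power is assumed.

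| f | Patients of 225 | r | m | Equivalent N | From 80% | From 90% |
|---|---|---|---|---|---|---|
| 1% | 2.25 | 0.5 | 0.995 | 222.8 | 79.6% | 89.7% |
| 1% | 2.25 | 1 | 0.990 | 220.5 | 79.2% | 89.4% |
| 2% | 4.5 | 0.5 | 0.990 | 220.5 | 79.2% | 89.4% |
| 2% | 4.5 | 1 | 0.980 | 216.1 | 78.4% | 88.8% |
| 5% | 11.25 | 0.5 | 0.975 | 213.9 | 78.0% | 88.5% |
| 5% | 11.25 | 1 | 0.950 | 203.1 | 75.9% | 86.9% |

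Worked example, last row: 2.8016 × 0.95 - 1.960 = 0.7015, and Φ(0.7015) = 75.9%.

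**Step 3. Sensitivity to the assumed share.** At f = 10% with full loss, m = 0.90, and 80% falls to 71.3%. The document gives no basis for choosing between 1% and 10%. A share at the low end seems more likely, since most ARB use is probably for blood pressure, but that is a judgement and not something the protocol states.

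**Step 4. After the change.** If any current ARB use excludes, f = 0 at entry, m = 1, and the assumed power is unchanged. No stated figure in the protocol moves.

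**The case against.** **The wording may be loose and not a deliberate carve-out.** Exclusion 1 is a single run-on item about antihypertensive treatment. Its closing words may only describe why ARBs are usually taken. Nothing in the protocol says that other ARB users are welcome. This stands: a reader might infer that the protocol knowingly admits them, and the text does not support that. The literal reading remains open all the same, and sites screen against the written words.

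**Some inclusion text cannot be read.** A figure directly under the inclusion heading is not shown, and the visible paragraph is numbered (ii). This also stands, so the point speaks for the visible text only.

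**The contrast with ACE-inhibitors can be overdrawn.** It is tempting to say that ACE-inhibitor users are shut out in every circumstance. The bar applies to current routine use, and the conversion wording suggests that a patient switched off the drug might enter. The difference that holds is narrower: one rule names no indication and the other does.

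**Existing safeguards reach part of the group.** A reason other than blood pressure implies another condition, which exclusion 5 may catch. A medical investigator is involved at Visit -1, and therapies and eligibility are checked again at baseline. This reduces the gap but does not close it, because exclusion 5 is discretionary and recording a drug does not exclude for it.

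**The harm is assumed.** The protocol gives no ARB share and does not say that an ARB weakens perindopril's effect on aneurysm growth. This stands in full and is why the figures are only illustrative.

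**Conclusion.** The point holds as a minor one. In the visible text the ARB exclusion is tied to an indication and the ACE-inhibitor bar is not, and no other visible rule reliably removes a patient on an ARB for another reason.

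The consequence depends on an assumption that is plausible but not stated in the document: that a concurrent ARB blunts perindopril's added effect. Given that, for assumed shares of 1-5% and half to full loss, an assumed 80% power falls to about 79.6-75.9%, and an assumed 90% to about 89.7-86.9%.

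Two stronger conclusions are not supported:

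- A reader might infer bias between arms. Randomisation balances such patients in expectation, so the effect is dilution.
- A reader might take some row of the table as an upper limit on the loss. Each result follows from the share chosen, and the document does not allow a bound.

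**What to change.** Delete from exclusion 1 the closing words that tie the ARB bar to blood pressure treatment, so that any current ARB use excludes. This aligns the rule with the one already applied to current ACE-inhibitor use, and the same wording can be carried into the definitive trial foreseen in Objective 2.

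The cost is one deleted phrase and a slightly smaller eligible pool: about 2 to 11 candidates per 225 under the assumed 1-5%. No new visit or data item is needed, because current therapies are already recorded at Visit -1 and checked at baseline.

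The change governs entry only. ARBs started during follow-up would be recorded in the existing therapies row but are not addressed by this edit.

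### EuroQoL is scheduled only after treatment starts, so follow-up scores cannot be adjusted for baseline and inexpensive precision is lost

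*Protocol*

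**What the plan says.** The visit schedule table at the end of the protocol has one combined row, "EuroQoL, health resource questionnaire". It carries two marks. Counted against the Months row, they fall at month 15 (Visit 6) and month 24 (Visit 9). The cells for Visits -2, -1 and 1 are empty, and no other text provides for a EuroQoL score before treatment.

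A baseline contact does exist. The table labels the month-0 visit "1 (Baseline) Either 1 week after blood test or 6 weeks after starting indapamide", and both ultrasound and blood pressure are marked there. Blood pressure is also marked at Visit -1. "Blood for creatinine and electrolytes" is marked at Visit -1 with a review at Visit 1.

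On the role of quality of life, Objective 2 says "Aneurysm-related mortality, morbidity and quality of life will be the major secondary end-points". That sentence concerns the later definitive trial. Objective 1, the pilot's own, names no quality-of-life end-point. On size, "The pilot trial will recruit approximately 225 patients", in three arms, with visits "every three months for a period of 24 months".

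**The concern.** A patient's questionnaire score before treatment usually predicts the same patient's later score. Using it as a covariate removes part of the between-patient variation from the treatment comparison. Without it, every between-arm EuroQoL estimate carries the full variance.

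The visit schedule is for the protocol to fix. An analysis plan can choose covariates, but it cannot create a measurement, and a pre-treatment score cannot be recovered once dosing has begun.

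The loss is one of precision, not bias. Chance imbalance between arms in starting quality of life could not be seen or adjusted for, and change from baseline could not be described. The pilot also could not estimate the baseline-to-follow-up correlation, which would help in sizing this end-point for the definitive trial. If the scores were ever used for quality-adjusted time, which the protocol does not state, the curve would have no starting value.

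**Working it through.** **Is there really no baseline mark?** The EuroQoL, Months and creatinine rows each have 13 cells, so they can be matched column by column:

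- EuroQoL: months 15 and 24.
- Creatinine: Visit -1 (mark), month 0 (review), then months 3, 12 and 24.
- Blood pressure: Visit -1, then every visit from month 0 to month 24.

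The creatinine and blood pressure rows fall into a sensible pattern, so the alignment is credible. If the first EuroQoL mark were one column out, it would sit at month 12 or 18, still well after treatment starts. The finding does not depend on its exact month.

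**What does the missing baseline cost?** The protocol gives no EuroQoL calculation, so there is no stated figure to reproduce.

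Inputs from the protocol: about 225 patients and three arms.

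Assumptions: equal allocation (225/3 = 75 per arm), two-sided 5% level, 80% power, no dropout at first, one follow-up score per patient, and a baseline-to-follow-up correlation r of 0.3, 0.5 or 0.7.

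Formulas, in units of the EuroQoL standard deviation (SD):

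- Standard error without baseline = √(2/75) = 0.163
- 95% half-width = 1.96 × √(2/75) × √(1 − r²)
- Difference detectable with 80% power = 2.8016 × √(2/75) × √(1 − r²)
- Patients per arm needed to match this precision without a baseline = 75/(1 − r²)

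| | Variance reduction | 95% half-width | Detectable difference | Equivalent n per arm |
|---|---|---|---|---|
| No baseline | – | 0.320 SD | 0.457 SD | 75 |
| r = 0.3 | 9% | 0.305 SD | 0.436 SD | 82 |
| r = 0.5 | 25% | 0.277 SD | 0.396 SD | 100 |
| r = 0.7 | 49% | 0.229 SD | 0.327 SD | 147 |

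Put as power: for a true difference of 0.457 SD, 80% without a baseline becomes 83.6%, 89.9% or 97.5%.

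**With incomplete return.** If only 60 per arm return questionnaires (an assumption), the half-width is 1.96 × √(2/60) = 0.358 SD without a baseline and 0.341, 0.310 or 0.256 SD with one.

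**With both follow-up scores averaged.** Suppose any two of the three scores have the same correlation r (an assumption). Relative to a single score, the variance of the two-score mean is (1 + r)/2 without a baseline and (1 + r)/2 − r² with one.

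- r = 0.3: 0.65 against 0.56, so half-widths of 0.320 × √0.65 = 0.258 and 0.320 × √0.56 = 0.240 SD
- r = 0.5: 0.75 against 0.50, so 0.277 and 0.226 SD
- r = 0.7: 0.85 against 0.36, so 0.295 and 0.192 SD

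The proportional saving in variance is then r²/[(1 + r)/2], that is 14%, 33% or 58%.

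**The case against.** The strongest objection is that no stated pilot objective is harmed. Objective 1 concerns aneurysm growth and blood-pressure-independent effects. Quality of life belongs to Objective 2, a later trial. The schedule gives no purpose for the EuroQoL row, and descriptive or feasibility use would fit the text as well as a between-arm comparison. This stands and limits the weight. It does not remove the point: the pilot already asks patients for EuroQoL, and feasibility or descriptive use would also be better served by a starting score.

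Second, the size rests on an unknown correlation. At r = 0.3 the half-width barely moves, from 0.32 to 0.31 SD. This also stands. Confidence is high that the mark is missing, but not about how much precision is lost.

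Third, two follow-up scores are scheduled, so the single-score figures are not exactly the precision the collected data would give. That is correct for the absolute widths. Under the equal-correlation assumption, however, averaging makes the proportional gain from a baseline larger.

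Fourth, the rows with pre-treatment values have their own reasons. Screening blood pressure, creatinine and aneurysm size decide eligibility, and the Visit 1 ultrasound starts the growth measurement. That is fair: the contrast between rows does not prove an oversight. It does show that a suitable visit exists.

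**Conclusion.** The point holds. As scheduled, EuroQoL is collected only on treatment, so its between-arm comparison is unbiased but cannot be baseline-adjusted, and no later document can repair that. With 75 per arm and a single follow-up score, the missing baseline leaves the variance without a reduction of 9% to 49% over the assumed range of r (25% at r = 0.5), equivalent to having about 82 to 147 patients per arm instead of 75. These figures depend on equal allocation and on r, neither of which the protocol states.

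This is a worthwhile, moderate improvement rather than an error that threatens the trial. It does not touch the growth-rate analysis, and the pilot declares no quality-of-life end-point of its own.

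**What to change.** In the visit schedule, add a EuroQoL mark at Visit 1 (Baseline), to be completed before the first dose. The health resource questionnaire shares the row but is not needed at baseline for this purpose, so split the row or add a footnote saying that the Visit 1 mark is for EuroQoL only. While editing the row, it is sensible to confirm that month 15 is the intended first follow-up point, though nothing above depends on it.

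The cost is one short questionnaire per patient, about 225 extra forms to enter, at a visit patients already attend. I would expect it to take a few minutes each. No extra visit or procedure is needed.
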